6.5.2. Analysis for Japan Submission

A subset of the planned efficacy, health outcomes, and safety analyses for Part B will be reproduced based on patients from Japan sites (Japanese population), in support of the regulatory

submission in Japan. The list of tables, listings, and figures for the Japanese population will be in a separate document.

6.5.3. Development Safety Update Report (DSUR)

The Development Safety Update Report (DSUR) is a required regulatory document that must be produced annually for LY3337641. The main objective of a DSUR is to present a comprehensive, thoughtful annual review and evaluation of pertinent safety information collected during the reporting period related to LY3337641. A reporting period will be defined. A dataset will be prepared including all randomized subjects with all variables related to safety update, such as gender, age, race, treatment arm, and information regarding whether the subject died or discontinued treatment due to an AE.

6.5.4. Clinical Trial Registry Analyses

Additional analyses will be performed for the purpose of fulfilling the Clinical Trial Registry (CTR) requirements. Since there can only be one set of AE tables, the label of the treatment arm will be including Parts of the study.

Analyses provided for the CTR requirements include summary of AEs, provided as a dataset which will be converted to an XML file. Both SAEs and ‘Other’ AEs are summarized by treatment group and MedDRA PT.

- An AE is considered ‘Serious’ whether or not it is a TEAE.
 - the number of occurrences causally related to treatment for Serious event
 - the number of fatalities for Serious event
 - the number of fatalities causally related to treatment for Serious event.
- An AE is considered in the ‘Other’ category if it is both a TEAE and is not serious. For each SAE and ‘Other’ AE, for each term and treatment group, the following are provided:
 - the number of participants at risk of an event
 - the number of participants who experienced each event term
 - the number of events experienced.
- Consistent with www.ClinicalTrials.gov requirements, ‘Other’ AEs that occur in fewer than 5% of subjects in every treatment group may not be included (5% is the minimum threshold).
- AE reporting is consistent with other document disclosures for example, the CSR, manuscripts, and so forth.

6.5.5. Analyses for the Optional Long-Term Extension Period

The objective of the optional long-term extension period is to collect long-term safety and efficacy data on LY3337641. For all subjects entering the long-term extension, the baseline visit is defined as Visit 106 in Part B.

Subjects will be grouped according to the treatment group in long-term extension and randomized treatment in Part B:

LY5mg(LTE)_Placebo(Part B); LY5mg(LTE)_LY5mg(Part B);

LY10mg(LTE)_Placebo(Part B); LY10mg(LTE)_LY10mg(Part B);
LY30mg(LTE)_Placebo(Part B); LY30mg(LTE)_LY30(Part B)

Unless otherwise specified, efficacy and health outcomes analyses will be conducted on the mITT population, defined as all randomized subjects receiving at least 1 dose of study drug. The analysis population (for applicable treatment outcome measures) will be all subjects with both a baseline and at least 1 postbaseline data measurement.

All variables and the change from baseline will be summarized by descriptive statistics. The statistics for continuous variables include mean, median, standard deviation, and number of observations. Categorical variables will be summarized by counts and percentages. No statistical hypothesis testing will be performed. The efficacy and health outcomes will be summarized as described in Section 6.3.

Safety analysis will be performed for all subjects entering the LTE, receiving at least 1 dose of the study drug and who do not discontinue the study for the reason “Lost to Follow-up” at the first postbaseline visit in LTE. The safety analysis will be conducted as described in Section 6.4. Duration of exposure will be calculated for each subject entering the LTE and summarized by treatment group for LTE period and cumulatively from Part B. Subjects who do not achieve response to study drug are eligible for rescue therapy at Week 16 and Week 20. From Week 24 onward, rescue therapy may be implemented for any subject determined to have ongoing active disease as assessed by the investigator. The safety, efficacy, and health outcome measures will be summarized separately for subjects who receive rescue therapies as described in Section 6.3 and Section 6.4.

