6.1.2. Baseline Definition

The baseline will be defined as the last available value before the first administration of study drug for both efficacy analyses, including unscheduled measurements for both parts separately. In most cases, this will be the measure recorded on Study Day 1 (Visit 2 in Part A and Visit 102 in Part B). Change from baseline values will be calculated as the postbaseline value minus the baseline value for each scheduled postbaseline time point. If the baseline value is missing (ie, no screening values, no Day 1 value, and no unscheduled measurements), the change from baseline will be missing as well.

For safety analyses, the baseline includes all pre-existing conditions recorded and any adverse events (AE) recorded before the first dose of study drug. Detailed definitions for each period of the studies are described in Section 6.4.2.

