6.3. Primary and Secondary Analyses

6.3.1. Primary Efficacy Analyses

The primary objective in Part A is safety (Section 6.4).

The primary efficacy assessment in Part B is the proportion of subjects who achieve an ACR20 response. To meet the ACR20 response, a subject must have at least 20% improvement from baseline in the following ACR core set components:

- TJC (68 joint count)
- SJC (66 joint count)
- At least 3 of the following 5 assessments:
 - 1) Physician's Global Assessment of Disease Activity (0-100 mm visual analog scale [VAS])
 - 2) Patient's Global Assessment of Disease Activity (0-100 mm VAS)
 - 3) Patient's assessment of pain (0-100 mm VAS)
 - 4) Patient's assessment of physical function as measured by the Health Assessment Questionnaire-Disability Index (HAQ-DI)
 - 5) Acute phase reactant as measured by hsCRP

Calculate ACR response (Responder, Non-responder, or Missing) at a visit will follow this algorithm:

Parameter	Abbreviation for the Parameter
% improvement in tender joint count	TJC68
% improvement in swollen joint count	SJC66
% improvement in Physician's Global Assessment of Disease Activity	PHYGA
% improvement in Patient's Global Assessment of Disease Activity	PATGA
% improvement in patient's assessment of pain	PATPain
% improvement in HAQ-DI	HAQ
% improvement in hsCRP	hsCRP

For all 7 parameters mentioned above, % improvement at a visit is calculated as:

$$(\text{baseline value} - \text{value at visit}) * 100 / \text{baseline value}.$$

Step 1: If the subject discontinued from the study prior to reaching a visit, assign ACR20 as Missing.

Otherwise, go to Step 2.

Step 2: If both TJC68 and SJC 66 are nonmissing and $\geq 20\%$, then go to Step 3. Otherwise,

If either TJC68 or SJC66 is nonmissing and $< 20\%$, then assign ACR20 as Non-Responder.

If both TJC68 and SJC66 are missing OR either TJC68 or SJC66 is nonmissing and the nonmissing value is $\geq 20\%$, then assign ACR20 as Missing.

Step 3: Consider the remaining 5 variables: PHYGA, PATGA, PATPain, HAQ, and hsCRP.

If ≥ 3 variables are missing, then assign ACR20 as Missing.

Otherwise, then proceed with the following order:

If ≥ 3 variables are $\geq 20\%$, then assign ACR20 as Responder.

If ≥ 3 variables are $< 20\%$, then assign ACR20 as Non-Responder.

If < 3 variables are $\geq 20\%$, then assign ACR20 response as Missing.

The number and percentage of subjects achieving ACR20 response over time will be summarized by treatment group.

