6.4.2. Adverse Events

Adverse events (AEs) will be classified by SOC and PT as defined by the MedDRA®.

A TEAE is defined as an event that first occurs or worsens in severity after baseline. The MedDRA Lowest Level Term (LLT) will be used in the treatment-emergent computation. The maximum severity for each LLT during the baseline period will be used as baseline. The Dosing Period will be included as postbaseline for the analysis. Events with a missing severity during the Dosing Period will be considered treatment-emergent. Events at baseline with missing severity and reports with severity change during the Dosing Period will be considered as treatment-emergent. For events occurring on the day of first taking study medication, the case report form (CRF)-collected flag will be used to determine whether the event was pre- versus post-treatment.

	Baseline	Postbaseline	Analysis
Part A			
Dosing Period	All pre-existing conditions recorded at Visit 1 and any AEs recorded before the first dose of study drug (during the interval between Visits 1 and 2 and recorded with the time of onset before the first dose of study drug)	Dosing period (during the interval between Visits 2 and 5)	All AE analyses
Follow-up	All AEs recorded during the last visit before discontinuing study drug.	Safety follow-up period (during the interval between Visits 5 and 801)	Only for post-exposure emergent AE by SOC and preferred term.
Part B			
Dosing Period	All pre-existing conditions recorded at Visit 101 and any AEs recorded before the first dose of study drug (during the interval between Visits 101 and 102 and recorded with the time of onset before the first dose of study drug)	Dosing period (during the interval between Visits 102 and 106)	All AE analyses
Follow-up	All AEs recorded during the last visit before discontinuing study drug.	Safety follow-up period (during the interval between Visits 106 and 802)	Only for post-exposure emergent AE by SOC and preferred term.
Long-term Extension			
Dosing Period	Any AEs recorded during the interval between Visits 105 and 106 and recorded with the time of onset before the first dose of study drug for the long-term extension.	Dosing period (during the interval between Visits 106 and 114)	All AE analyses
Follow-up	All AEs recorded during the last visit before discontinuing study drug.	Safety follow-up period (during the interval between Visits 114 and 805)	Only for post-exposure-emergent AE by SOC and preferred term.

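### SAP 6.5.5 gives the extension one efficacy baseline, Week 12, so responder measures in the continuing-LY3337641 groups count only improvement beyond Week 12

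*SAP*

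**What the plan says.** SAP 6.5.5 gives the extension's purpose as collecting long-term safety and efficacy data. It sets the reference, "For all subjects entering the long-term extension, the baseline visit is defined as Visit 106 in Part B", and then says: "The efficacy and health outcomes will be summarized as described in Section 6.3". It also says: "All variables and the change from baseline will be summarized by descriptive statistics". Results are laid out in six groups, defined by extension dose and Part B randomized arm, and no hypothesis is tested.

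SAP 5.1 makes the Week 12 visit both the end of Part B dosing and the first extension visit. Subjects on LY3337641 stay on their dose. Placebo subjects are rerandomized 1:1:1 to 5, 10 or 30 mg at that visit.

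Four other places bear on the point:

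- SAP 6.3.1: "For all 7 parameters mentioned above, % improvement at a visit is calculated as" the baseline value minus the visit value, times 100, divided by the baseline value.
- SAP 6.1.2: the general efficacy baseline is the last value before the first dose, "including unscheduled measurements for both parts separately".
- SAP 6.4.2: the extension has its own adverse-event baseline, "Any AEs recorded during the interval between Visits 105 and 106", limited to onset before the first extension dose.
- SAP 6.5.5, on exposure: duration is "summarized by treatment group for LTE period and cumulatively from Part B". Efficacy has no such second reference.

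**The concern.** In the continuing groups the reference value is itself an on-treatment value. Every measure defined relative to baseline then asks whether the subject improved again after Week 12, not whether the Part B response lasted. Durability of response is the natural efficacy question for these groups, and SAP 6.5.5 does not plan an ACR, EULAR or MCID rate that answers it relative to the pre-treatment state.

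Two misreadings are at stake. A low responder rate in a continuing group could be taken as lost efficacy when disease is unchanged. And a switching group could look better than a continuing group at the same disease level, because the two sit in one table with references of different meaning.

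**Working it through.** The plan states no efficacy figure for the extension, so there is none to reproduce. The Part B power calculation does not enter.

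**Inputs from the SAP.** The percent-improvement formula (6.3.1); ACR cut-offs of 20, 50, 70 and 90%; EULAR improvement bands of >1.2, >0.6 to 1.2, and ≤0.6 (Table JPDA.6.3); the DAS28-hsCRP formula with constant 0.96 (6.3.3.2); MCIDs of ≥2.50 for the SF-36 summary scores and ≥3.56 for FACIT-F (6.3.4.3, 6.3.4.4); 61 subjects per arm and 244 in all (5.2).

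**1. A held response.** The tender joint counts below are illustrative and not from the documents.

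| Subject | Visit 102 | Visit 106 | Extension | From Visit 106 | From Visit 102 |
|---|---|---|---|---|---|
| Continuing, held | 20 | 8 | 8 | (8−8)×100/8 = 0% | (20−8)×100/20 = 60% |
| Continuing, slightly worse | 20 | 8 | 10 | (8−10)×100/8 = −25% | (20−10)×100/20 = 50% |
| Switching | 20 | 20 | 8 | 60% | 60% |

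If all seven components are nonzero at Visit 106 and held exactly, all seven percentages are 0. The subject is a Non-Responder at every ACR level, with ACR-N 0 and hybrid ACR 0. A held DAS28-hsCRP is an improvement of 0, which is EULAR No Response. A held SF-36 or FACIT-F score is a change of 0, below either MCID.

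**2. What is needed to count.** Let x be the improvement at Week 12 and t the ACR cut-off, and assume all components move by the same fraction. The improvement needed from Day 1 is 1 − (1−x)(1−t).

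| x | ACR20 | ACR50 | ACR70 |
|---|---|---|---|
| 20% | 36% | 60% | 76% |
| 50% | 60% | 75% | 85% |
| 70% | 76% | 85% | 91% |

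**3. Two subjects at the same disease level.** Both are 50% better than Day 1 at an extension visit. A continuing subject who was already 50% better at Week 12 scores 1 − 0.50/0.50 = 0%. A switching subject who was 10% better at Week 12 scores 1 − 0.50/0.90 = 44%, an ACR20 response.

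**4. EULAR floor.** With all four inputs at zero, DAS28-hsCRP is 0.96. Good Response needs an improvement above 1.2, which is impossible from a Visit 106 score at or below 0.96 + 1.2 = 2.16. Any response needs more than 0.6, which is impossible from 0.96 + 0.6 = 1.56 or below. These are the best-controlled subjects; if held, they still count as remission (<2.6).

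**5. Zero at Visit 106.** The formula then divides by zero, and the SAP does not say what follows. Suppose, as an assumption, that an undefined percentage is treated as missing. The Missing branch of Step 2 opens "If both TJC68 and SJC66 are missing OR either TJC68 or SJC66 is nonmissing" and goes on to require that the nonmissing value be at least 20%. Two zero counts therefore give Missing. One zero count gives Missing or Non-Responder, depending on the other count. Neither case can reach Responder.

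**6. How many subjects.** The number entering the extension is not given. Planned continuing subjects cannot exceed 3 × 61 = 183 of 244 (75%), because only Part B completers are eligible and entry is optional.

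**The case against.** The strongest reply is that Visit 106 is a deliberate and legitimate choice. The SAP treats the extension as a separate period with its own adverse-event baseline, and change since extension entry is a proper question. For the switching groups Visit 106 is the right reference. This stands, which is why the Visit 106 summaries should stay. A reader might infer that 6.5.5 breaks 6.1.2; it does not, since 6.1.2 covers Parts A and B.

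Second, maintenance is partly visible already. Observed values are summarized by visit, remission, low disease activity and DAS28 categories use absolute cut-offs, and a change near zero from Visit 106 shows that the Week 12 level was kept. This also stands. A reader might infer that the extension output hides durability altogether; that goes too far. What is missing is the proportion still in ACR, EULAR or MCID response relative to pre-treatment. Part B reports Week 12 ACR response, but not for extension entrants alone or at later visits.

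Third, nothing is tested, no contrast of continuing with switching groups is planned, and the groups are labelled by Part B arm. This limits the harm but does not remove it, because descriptive rates are all the efficacy output that the extension has.

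Fourth, the extension is governed by Protocol Addendum 1, which was not supplied. The point is therefore confined to SAP 6.5.5. It cannot be said that no pre-treatment-referenced table is planned anywhere.

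**Conclusion.** The point holds for baseline-relative efficacy and health-outcome measures in the three continuing-LY3337641 groups. With Visit 106 as the sole stated reference, SAP 6.5.5 gives a misleading summary, or none, of response maintained relative to pre-treatment. It also gives responder rates that are not comparable between continuing and switching groups. Part B analyses are untouched. The data are already collected and the tables could be recomputed later, so this is a moderate reporting defect.

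The 0% result needs nonzero values at Visit 106. The thresholds in step 2 need equal fractional movement of all components. The EULAR limits need only the SAP's formula and table.

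Two stronger readings are not supported. One is that every held response becomes a Non-Responder: with zero joint counts the result is undefined, or Missing if undefined is treated as missing. The other is that some stated share of maintained responders would be misclassified. The documents say nothing about how disease varies after Week 12, so any such rate would rest on invented inputs, and none is given here.

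Separately, the note under Figure JPDA.5.2 defines response at Weeks 16 and 20 as 20% improvement in either joint count from a baseline that it does not name, and links non-response to rescue eligibility. That note and the 6.5.5 baseline must be reconciled by the sponsor.

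**What to change.** In SAP 6.5.5:

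- Add descriptive summaries of the baseline-relative measures (ACR responses, ACR-N, hybrid ACR, EULAR response, MCID rates and change scores) referenced to the Part B pre-dose baseline, meaning the last value before the first Part B dose, normally Visit 102. Show them for all six groups.
- Keep the summaries referenced to Visit 106.
- Label each table with the baseline that it uses.
- State how a zero value at Visit 106 is handled in percent-improvement measures.
- Name the baseline in the Figure JPDA.5.2 note and reconcile it with 6.5.5.

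The cost is SAP wording, one extra derived baseline and more descriptive tables. No new data are needed. Specifying the second reference now also avoids choosing it after results are seen.

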The optional long-term extension period will allow eligible subjects who complete Part B of Study JPDA to receive up to an additional 52 weeks of LY3337641. Subjects who complete the 12-week dosing period of Study JPDA Part B and who, in the opinion of the investigator, have no condition that would preclude continued participation in the study, will be eligible to participate in the extension. The last visit of the dosing period of Study JPDA Part B (Week 12, Part B) will also serve as the initial visit for the extension (Week 12, extension). Subjects who decide to participate in this addendum will not have the 2-week post-treatment safety follow-up period visit in Part B, but will enter the long-term extension period instead and have their 2-week safety follow-up visit at the end of the long-term extension period (Visit 805). Subjects will sign a separate informed consent form to enroll in the long-term extension period.

All subjects originally randomized to any dose of LY3337641 in Study JPDA Part B will continue on their current dose in the long-term extension. All subjects originally randomized to placebo in Study JPDA Part B will be rerandomized at the initial visit of the extension (Week 12) in a 1:1:1 ratio to receive 5, 10, or 30 mg of LY3337641. The entire long-term extension period will remain double-blind, as the dose of LY3337641 will remain blinded to the site and subjects. This addendum is considered unblinded to the sponsor once the main study is unblinded (see [Figure JPDA.5.2](#)).

Part A

[figure not shown]

Part B

Note: There will be an interim unblinded safety analysis by an assessment committee at least 2 weeks after all subjects have had their last dose in Part A. If a decision to proceed with the study is made, Part B will start enrolling new subjects. Part A subjects cannot participate in Part B.

Figure JPDA.5.1. Illustration of the study design for Clinical Protocol I8K-MC-JPDA.

*At Weeks 16 and 20, subjects who achieve at least a 20% improvement from baseline in either the tender or swollen joint count will be considered responders. Subjects who do not achieve response to study drug by this criterion will be eligible for rescue therapy. Starting at Week 24, rescue therapy may be implemented for any subject determined to have ongoing active disease as assessed by the investigator.

Figure JPDA.5.2. Illustration of the study design for optional long-term extension addendum of Clinical Protocol I8K-MC-JPDA(1).

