5.2. Determination of Sample Size

Approximately 32 at least mildly active RA subjects will be enrolled and randomly assigned in a 1:1:1:1 ratio to 1 of the 3 doses of LY3337641 (5, 10, or 30 mg) or placebo in Part A. This sample size is customary for evaluating safety and PK and/or PD parameters, and is not powered on the basis of statistical hypothesis testing.

Approximately 244 moderately to severely active RA subjects will be enrolled and randomly assigned in a 1:1:1:1 ratio to 1 of the 3 doses of LY3337641 (5, 10, or 30 mg) or placebo in Part B. All subjects who discontinue the treatment early (before Week 12) will be considered as failing the primary endpoint in Part B. The sample size of 61 subjects per arm will provide at least 80% power at the 2-sided .05 significance level to detect a difference of 25% in the primary endpoint (ACR20 response rate at Week 12) between each LY3337641 dose and placebo, assuming a 30% placebo response rate.

If the assessment committee determines that a dose adjustment is needed, the total study sample size may be adjusted.

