For events that are sex specific, the denominator and computation of the percentage will only include subjects of the given sex. Otherwise, percentages will be calculated using the safety population as the denominator. Adverse events will be summarized as TEAEs.

In an overview table, the number and percentage of subjects who experienced a TEAE or serious adverse event (SAE), died due to an AE, or discontinued from study due to an AE will be summarized by treatment.

The frequency and percentages of subjects with TEAEs will be summarized by treatment using MedDRA PT nested within SOC. Events will be ordered by decreasing frequency within SOC. A common TEAEs (at least reported by 5% of subjects) summary will also be provided. As an additional table or figure, the percentages of subjects with TEAEs will be summarized by treatment using MedDRA PT (without regard to SOC). Events will be ordered by decreasing

frequency within PT. The frequency and percentages of subjects with TEAEs by maximum severity will also be summarized by treatment using MedDRA PT nested within SOC.

Fisher's exact test will be performed to compare percentages for each LY3337641 dose group and Placebo at both the SOC and PT levels.

Listings will be presented for all AEs, all SAEs, all AEs leading to death, all AEs leading to study drug temporary interruption, and all AEs leading to discontinuation from the study.

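### The long-term extension's adverse events are planned only as subject percentages in six split groups; pooled columns and exposure-adjusted rates would serve its long-term safety objective better at little cost

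*SAP*

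**What the plan says.** SAP 5.1 describes an optional extension for Part B completers. Subjects on LY3337641 stay on their dose, and placebo subjects "will be rerandomized at the initial visit of the extension (Week 12) in a 1:1:1 ratio" to 5, 10 or 30 mg. Treatment can run a further 52 weeks.

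SAP 6.5.5 names long-term safety and efficacy as the objective and fixes the columns: "Subjects will be grouped according to the treatment group in long-term extension and randomized treatment in Part B". Six combinations are listed, each dose being split into former placebo and same-dose subjects. Categorical results are counts and percentages, without hypothesis tests, and safety follows Section 6.4. There, for events that are not sex specific, "percentages will be calculated using the safety population as the denominator". In the table in 6.4.2 the postbaseline window for the extension reads "Dosing period (during the interval between Visits 106 and 114". Its baseline is the adverse events recorded between Visits 105 and 106.

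SAP 6.5.5 also summarizes duration of exposure by group, both for the extension alone and cumulatively from Part B, and reports subjects who receive rescue separately. Neither section plans a column pooled by current dose, an all-LY3337641 column, a person-time rate or a confidence interval for an extension adverse-event rate.

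**The concern.** The extension is the only part of the study with more than 12 weeks of dosing, so it carries the long-term safety information. The planned display weakens that information in three ways.

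- **Small columns.** The former placebo arm is divided by three. An empty cell in a switch column then says little about risk, although subjects on the same dose sit in the next column.
- **Unequal time at risk.** Subjects may stop at any time over 52 weeks. A percentage of subjects ignores this, so two doses with the same underlying rate can look different, or a worse dose can look equal.
- **No adverse-event table over all active-drug time.** For continuing subjects exposure is cumulated from Part B, but extension events start at Visit 106. An event that first arose on LY3337641 between Visits 105 and 106 is baseline and counts again only if it worsens. Part B tables cover the first 12 weeks separately.

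At stake is how clearly the extension describes risk by dose. The randomized Part B comparisons are untouched.

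**Working it through.** **The plan's own figure.** SAP 5.2 states: "The sample size of 61 subjects per arm will provide at least 80% power at the 2-sided .05 significance level" for a 25-point difference, "assuming a 30% placebo response rate". With p1 = 0.30, p2 = 0.55 and mean 0.425:

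n = [1.960 × √(2 × 0.425 × 0.575) + 0.842 × √(0.30 × 0.70 + 0.55 × 0.45)]² / 0.25² = 60.2, so 61 per arm; power at 61 is 80.5%.

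The figure reproduces. It concerns Part B efficacy; the documents give no size or precision target for the extension.

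**Group sizes.** If every Part B subject entered, a switch group would have 61/3 = 20.3, about 20. A continuing group would have 61, a dose pooled 61 + 20 = 81, and the whole extension 4 × 61 = 244. These are upper bounds, because entry is optional and limited to completers. An entry rate of 75% is assumed below to show the range.

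**Precision with zero events.** The exact two-sided 95% upper limit is 1 − 0.025^(1/n). The chance of seeing at least one case of an event with a true 2% risk is 1 − 0.98^n.

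| Column | n, all enter | Upper limit | Chance of ≥1 case at 2% risk | n, 75% enter | Upper limit |
|---|---|---|---|---|---|
| Switch group | 20 | 16.8% | 33% | 15 | 21.8% |
| Continuing group | 61 | 5.9% | 71% | 46 | 7.7% |
| Pooled by dose | 81 | 4.5% | 81% | 61 | 5.9% |
| All LY3337641 | 244 | 1.5% | 99% | 183 | 2.0% |

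**Crude percentage under unequal stopping.** Assume a constant event hazard λ and an unrelated constant stopping hazard μ over one year, with μ = −ln(1 − proportion stopped). Then

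crude percentage = λ/(λ + μ) × [1 − exp(−(λ + μ))].

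With λ = 0.30 per person-year:

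- 10% stop: μ = 0.105, so 0.30/0.405 × 0.333 = 24.7%.
- 50% stop: μ = 0.693, so 0.30/0.993 × 0.630 = 19.0%.

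Events divided by person-years to first event or stopping return 30 per 100 person-years in both cases (0.2466/0.822 and 0.1902/0.634). Conversely, a dose with 50% stopping and a true rate of about 41 per 100 person-years also shows 24.7%. The documents give no stopping rates.

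**The same check for an early-onset event.** Confine the risk to the first 4 weeks, with hazard 3.9 per person-year and the same two stopping levels. Crude percentages are 25.8% and 25.3%, almost equal. The exposure-adjusted rates are 0.2582/0.7126 = 36 and 0.2527/0.5437 = 46 per 100 person-years. Here the crude percentage is nearly right, and the rate makes the early-stopping dose look worse than it is.

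**The case against.** The strongest reply is that this is an uncontrolled, descriptive Phase 2 extension and that most of the information is already on the page.

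- **Counts can be added.** The six groups are mutually exclusive and counts are reported, so totals by dose and overall follow by addition. This stands for subject percentages. It does not recover person-time to first event.
- **Exposure is shown.** A reader might infer that no exposure summary matches the extension adverse-event window. The documents do not support that: SAP 6.5.5 summarizes exposure for the extension period as well as cumulatively, in the same groups. For switch subjects that is all their LY3337641 time. What is missing is a rate that uses the exposure and, for continuing subjects, an adverse-event table from first dose to match the cumulative exposure.
- **Bias is not certain.** A reader might infer that a dose stopped early must look safer for every event. It need not: the calculation above shows little effect for early-onset events. An adverse event that causes stopping is still counted, and discontinuations due to adverse events have their own table (SAP 6.4.2.2).
- **Not every column is tiny.** The figure of about 20 applies to switch groups only. Pooling moves a continuing group's zero-event limit only from 5.9% to 4.5%.
- **Other outlets exist.** SAP 6.1 allows exploratory analyses, and 6.5.3 and 6.5.4 cover the annual safety report and registry tables. None of these prespecifies pooled-dose columns or person-time rates. The extension addendum was not among the documents, so the point concerns what the SAP prespecifies.

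**Conclusion.** The point holds as a cheap improvement to the reporting plan. For a period whose stated objective includes long-term safety, the SAP prespecifies adverse-event summaries only in six split groups and only as percentages of subjects.

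The cost in precision is large for the switch groups (16.8% at n = 20 against 4.5% pooled by dose) and modest for the continuing groups. These sizes assume full entry; lower entry widens every limit.

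The distortion from unequal stopping is conditional. In the constant-hazard example it is 24.7% against 19.0% for the same true rate. That rests on assumed stopping of 10% and 50%, a continuing hazard, and stopping unrelated to the event. For early-onset events it is near zero. No Part B conclusion depends on this.

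**What to change.** In SAP 6.5.5 keep the six groups and the crude percentages. For TEAEs, SAEs, rash, infections and discontinuations due to adverse events, add:

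1. columns pooled by extension dose (5, 10 and 30 mg) and over all LY3337641;
2. exposure-adjusted incidence per 100 person-years with a 95% CI, with time censored at the first event;
3. one all-LY3337641 set that counts events and time from the first LY3337641 dose: Part B Day 1 for subjects randomized to LY3337641, Visit 106 for those switched from placebo.

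State whether events and time after rescue enter these displays, since 6.5.5 reports rescued subjects separately.

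The cost is SAP wording and a few columns or tables from data already collected; conduct does not change. Two downsides should be written next to the tables. Pooled columns mix subjects who already tolerated 12 weeks of drug with new starters; the retained six-group display shows this. A constant-rate adjustment can also overstate risk for front-loaded events, which may include rash, in a dose with early stopping. The rates must therefore be read beside the crude percentages.
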